3.3.1.2 Exclusion Criteria

Patients who meet any of the following criteria will not be eligible to participate in the study:

- 1. Patient has a history of complete lack of GERD symptom response to PPIs.
- 2. Patient reports epigastric pain or epigastric burning as his or her predominant symptom at the Screening Visit.
- 3. Patient has a diagnosis of gastroparesis per gastric emptying study, or a history of bowel obstruction, or is at risk for a bowel obstruction (eg, patient has an organic gastrointestinal [GI] motility disorders or a history of major GI surgery).
- 4. Patient has a history of serum triglyceride concentrations > 500 mg/dL on a fasting specimen, or has serum triglyceride concentrations > 500 mg/dL on a fasting specimen at Screening or any time during the Pretreatment Period.
- 5. Patient has a history of hypertriglyceridemia-induced pancreatitis.
- 6. In the Investigator's opinion, patient is susceptible to a deficiency of fat-soluble vitamins (especially vitamin D deficiency; eg, the patient has osteoporosis or osteomalacia) and will be put at risk by receiving colesevelam for 8 weeks.
- 7. Patient has an active swallowing disorder that would compromise their ability to swallow the study medication.
- 8. Patient has any alarm symptoms including, but not limited to, GI bleeding, anemia, vomiting, or unexpected weight loss at any time during the Screening or Pretreatment Periods.
- 9. Patient has undergone surgery that meets any of the following criteria:
 - a. Surgery of the GI tract (including gastric banding) other than an appendectomy, cholecystectomy, or minor oral or rectal surgery (eg, tonsillectomy, hemorrhoidectomy, rectocele repair) at any time before the Screening Visit
 - b. An appendectomy during the 3 months before the Screening Visit, or a cholecystectomy during the 6 months before the Screening Visit, or minor oral or rectal surgery during the 30 days before the Screening Visit

- c. Non-GI surgery of the abdomen, pelvis, or retroperitoneal structures during the 6 months before the Screening Visit
- d. Thoracic surgery during the 6 months before the Screening Visit
- e. Other major non-GI surgery during the 30 days before the Screening Visit
- 10. Patient has previously undergone thoracic or abdominal radiotherapy.
- 11. Patient has large (>5 cm) hiatal hernia.

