3.5.6 Clinical Laboratory Determinations

Blood and urine samples for clinical laboratory tests will be collected at the visits defined in the Schedule of Evaluations within the protocol synopsis. The clinical laboratory evaluations will include the clinical chemistry, hematology, coagulation, and urinallysis parameters presented in Table 3.

Table 3. Clinical Laboratory Tests

Clinical Chemistry	Hematology (CBC)	Complete Urinalysis
Albumin	Hematocrit	pH and specific gravity
Alkaline phosphatase	Hemoglobin	Bilirubin
ALT	Platelet count	Glucose
AST	MPV	Ketones
Bicarbonate	RBC count	Leukocytes
BUN	WBC count	Nitrites
Calcium	WBC differential	Occult blood
Chloride	(% and absolute)	Protein
Total cholesterol	Basophils	Urobilinogen
HDL cholesterol	Eosinophils	
LDL cholesterol	Lymphocytes	
Creatinine	Monocytes	
GGT	Neutrophils	
Glucose	RBC indices	
HbA1C	MCH	
Iron	MCHC	
LDH	MCV	
Magnesium	RDW	
Phosphorus	Coagulation	
Potassium	aPTT	
Sodium	PT	
Total bilirubin		
Total protein		
Triglycerides		
Uric acid		

Abbreviations: ALT = a lanine a minotransfera se; a PTT = activated partial thromboplast in time; AST = a spartate a minotransfera se; BUN = blood urea nitrogen; CBC = complete blood count; GGT = gamma glutamyl transfera se; HbA1C = glycated hemoglobin; HDL = high-density lipoprotein; LDH = lactate dehydrogenase; LDL = low-density lipoprotein; MCH = mean corpuscular hemoglobin; MCHC = mean corpuscular hemoglobin concentration; MCV = mean corpuscular volume; MPV = mean platelet volume; PT = prothrombin time; RBC = red blood cell; RDW = red cell distribution width; WBC = white blood cell

A pregnancy test will be administered to all female patients of childbearing potential (ie, women who are not postmenopausal or who have not had a bilateral oophorectomy, hysterectomy, or tubal ligation) at the Screening, Randomization (prior to dosing), Week 4, and EOT Visits. These pregnancy test results must be negative for patient eligibility. All positive urine pregnancy tests results will be confirmed by a serum pregnancy test.

A urine screen for selected drugs of abuse (cocaine, barbiturates, amphetamines, opiates, benzodiazepines, cannabinoids, and phencyclidine) and a serum alcohol screen will be performed at the Screening Visit.

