5.5.6. Clinical Laboratory Data

Blood and urine samples for clinical laboratory tests will be collected at the visits defined in the Schedule of Evaluations (Appendix 4). The clinical laboratory tests for hematology, chemistry, urinalysis, coagulation, pregnancy test and drug screening will be performed. For details refer to Clinical Study Protocol C3718-301, Section 3.5.6.

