7.10.2. Clinical Laboratory Parameters

Descriptive statistics for clinical laboratory values (in SI units) and changes from the baseline values at each assessment time point will be presented by treatment group for each clinical laboratory parameter. All laboratory data will be listed. The clinical laboratory parameters are listed in Section 5.5.6.

For each clinical laboratory parameter, the number and percentage of patients with potentially clinically significant (PCS) postbaseline clinical laboratory values will be tabulated by treatment group for data collecting no more than 1 day after the last dose. The criteria for PCS laboratory values are described in Table 8. The percentages will be calculated relative to the number of patients with available non-PCS baseline values and at least 1 post-baseline assessment. The

potential numerator will be the total number of patients with available non-PCS baseline values and at least 1 post-baseline PCS value in the corresponding postbaseline period.

A supportive listing for patients with PCS postbaseline values will be provided, including the PID number, study center, baseline and postbaseline values for each visit, and a flag indicating the PCS laboratory values.

Parameter	SI Unit	Lower Limit	Higher Limit
CHEMISTRY	· ·		I
Albumin	g/L	<0.9 × LLN	>1.1 × ULN
Alanine aminotransferase	U/L	_	$\geq 3 \times ULN$
Alkaline phosphatase	U/L	_	$\geq 3 \times ULN$
Aspartate aminotransferase	U/L	_	$\geq 3 \times ULN$
Bicarbonate	mmol/L	<0.9 × LLN	>1.1 × ULN
Bilirubin, total	μmol/L	_	>1.5 × ULN
Calcium	mmol/L	<0.9 × LLN	>1.1 × ULN
Chloride	mmol/L	<0.9 × LLN	>1.1 × ULN
Cholesterol, total	mmol/L		>1.6 × ULN
Creatinine	μmol/L	_	>1.3 × ULN
Glucose	mmol/L	<0.8 × LLN	>1.4 × ULN
Magnesium	mmol/L	<0.9 × LLN	>1.1 × ULN
Phosphate	mmol/L	<0.9 × LLN	>1.1 × ULN
Potassium	mmol/L	<0.9 × LLN	>1.1 × ULN
Protein, total	g/L	<0.9 × LLN	>1.1 × ULN
Sodium	mmol/L	<0.9 × LLN	>1.1 × ULN
Urea nitrogen	mmol/L	_	>1.2 × ULN
Uric acid	µmol/L	<0.9 × LLN	>1.1 × ULN
HEMATOLOGY	· ·		
Basophils, absolute cell count	10 ⁹ /L	_	>3 × ULN
Eosinophils, absolute cell count	10 ⁹ /L		>3 × ULN
Hematocrit	Ratio	<0.9 × LLN	>1.1 × ULN

 Table 8:
 Criteria for Potentially Clinically Significant Laboratory Results

Parameter	SI Unit	Lower Limit	Higher Limit
Hemoglobin	g/L	<0.9 × LLN	>1.1 × ULN
Lymphocytes, absolute cell count	10 ⁹ /L	<0.8 × LLN	>1.5 × ULN
Mean corpuscular hemoglobin	Pg	_	>3 × ULN
Mean corpuscular hemoglobin concentration	g/L	_	>3 × ULN

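### SAP Table 8 gives abnormality criteria for 31 of the 42 blood parameters that SAP 7.10.2 promises to count; triglycerides, PT and aPTT are among the missing, and the MCH and MCHC limits are uninformative

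*SAP*

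**What the plan says.** SAP 7.10.2 sets the scope of the abnormal-value table: "For each clinical laboratory parameter, the number and percentage of patients with potentially clinically significant (PCS) postbaseline clinical laboratory values will be tabulated". The limits come from one place: "The criteria for PCS laboratory values are described in Table 8". For the list of parameters, 7.10.2 refers to SAP 5.5.6, which passes the reader on: "For details refer to Clinical Study Protocol C3718-301, Section 3.5.6". Protocol 3.5.6 then states: "The clinical laboratory evaluations will include the clinical chemistry, hematology, coagulation", plus urinalysis, and itemises the tests in protocol Table 3. Triglycerides are listed under chemistry, and PT and aPTT under coagulation. The Schedule of Evaluations places laboratory draws at Screening, Randomization, Week 4 and End of Treatment.

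Table 8 has a chemistry block and a hematology block. It has no coagulation block and no triglyceride row. MCH and MCHC have no lower limit and an upper limit of >3 x ULN. MCV, in the next row, has <0.9 x LLN and >1.1 x ULN.

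The protocol treats high triglycerides as a reason not to enrol. Exclusion 4 in section 3.3.1.2 covers past values, "Patient has a history of serum triglyceride concentrations > 500 mg/dL on a fasting specimen", and applies the same fasting limit to the sample drawn for eligibility. Exclusion 5 reads "Patient has a history of hypertriglyceridemia-induced pancreatitis".

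**The concern.** A PCS table answers a question that means do not: how many patients in each arm, starting from an acceptable value, crossed a fixed limit on treatment. Its denominator in SAP 7.10.2 is patients with a non-PCS baseline, so it is built to pick up new on-study abnormalities. A parameter with no limit cannot enter it, and a parameter with an unreachable limit enters it as zero in both arms whatever happens.

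Following the SAP exactly therefore has two consequences. The promised table cannot be produced for 11 blood tests, one of which is the test behind two of the protocol's own exclusions. And two rows would report no abnormality in either arm, which a reader could take for reassurance. Limits added once treatment codes are known would be post hoc.

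**Working it through.** There is no power, alpha or sample-size figure to reproduce. Two checks apply.

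**1. Coverage: protocol Table 3 against SAP Table 8**

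| Block | Protocol Table 3 | SAP Table 8 | No PCS criterion |
|---|---|---|---|
| Chemistry | 25 | 18 | HDL, LDL, GGT, HbA1C, iron, LDH, triglycerides (7) |
| Hematology, each differential cell type counted once | 15 | 13 | MPV, RDW (2) |
| Coagulation | 2 | 0 | aPTT, PT (2) |
| Total | 42 | 31 | 11 |

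42 - 31 = 11. Every row of Table 8 matches a protocol test, so the mismatch runs one way. No urinalysis parameter has a criterion either.

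**2. Can the MCH and MCHC limits be reached?**

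Table 8 takes the ULN from the laboratory, and neither document gives a value. The ranges below are assumptions.

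- MCHC, assumed ULN 340-370 g/L. Limit = 3 x ULN: 3 x 340 = 1020 g/L to 3 x 370 = 1110 g/L. Against an assumed red-cell mass density of 1100 g/L, that is 1020/1100 = 93% to 1110/1100 = 101%. The cell would have to be almost pure hemoglobin, so the limit is not attainable.
- MCH, assumed ULN 31-35 pg. Limit: 3 x 31 = 93 pg to 3 x 35 = 105 pg. Since MCH (pg) = MCV (fL) x MCHC (g/L) / 1000, the MCV needed with MCHC at 340-370 g/L runs from 93 x 1000/370 = 251 fL to 105 x 1000/340 = 309 fL.
- Without units: with MCHC at its ULN, MCV would have to be 3 times the ratio of the MCH ULN to the MCHC ULN. Table 8 already flags MCV at 1.1 x ULN. The MCH limit is not arithmetically impossible, but in practice it would not be met.

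Basophils, eosinophils and monocytes carry the same form of limit (no lower bound, >3 x ULN). That form can work for a cell count, which can rise several-fold. It does not work for a red-cell index.

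**Triglyceride figure in the SAP's units.** Section 7.10.2 reports in SI units: 500 mg/dL x 0.01129 = 5.645, or 5.65 mmol/L (standard conversion factor, not given in the documents).

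**The case against.** The strongest reply is that little is lost, and much of it stands.

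- **The omitted tests are reported elsewhere.** SAP 6.1 defines descriptive statistics to include SD, minimum and maximum, and 7.10.2 applies them to each laboratory parameter with a full listing. Protocol 3.5.1.2 and 3.5.1.4 make a laboratory abnormality an adverse event if it is clinically significant or needs treatment, and SAP 7.10.1 counts such events by arm. A reader might infer that the trial would never look at triglycerides or clotting tests, or would show them only as mean changes. That is not so. These displays still do not give the number per arm crossing a fixed limit, and adverse-event capture depends on the investigator's judgment.
- **No exclusion concerns clotting.** A reader might infer one from exclusion 6, "patient is susceptible to a deficiency of fat-soluble vitamins", or from the warfarin prohibition in protocol Appendix 4. Exclusion 6 singles out vitamin D and gives bone disease as its examples. Warfarin is listed for drug interaction and narrow therapeutic index. The case for PT and aPTT rests only on their being collected and promised a count.
- **The 500 mg/dL limit is a fasting limit.** Protocol 3.4.6 and 3.6.2 have patients take study drug after breakfast and before attending on-treatment visits, so Week 4 and End of Treatment samples are largely non-fasting. Schedule note j makes a fasted repeat optional. This limits how a triglyceride count can be read; it does not remove its use as a comparison between arms.
- **Red-cell abnormality is still flagged.** Hemoglobin, hematocrit, red-cell count and MCV all have 0.9 x LLN and 1.1 x ULN limits in Table 8, so the weak MCH and MCHC rows cost little.
- **Phase 2b showed no signal.** Protocol 1.3 reports no clinically significant treatment-attributable laboratory change other than lower total cholesterol and LDL-C. That lowers the expected yield but does not supply the missing limits.
- **The protocol promised less.** Protocol 3.7.5.2 commits only to descriptive statistics and change from baseline. The inconsistency is between the SAP's own sentence and its own table, and is not a breach of the protocol.

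**Conclusion.** The point holds as a defect in safety reporting. Table 8 leaves 11 of 42 blood parameters without a criterion although SAP 7.10.2 promises a count for all. Triglycerides matter most among them because of exclusions 4 and 5. The MCH and MCHC limits are the clearest error.

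That second conclusion rests on assumed ULNs. Over the ranges shown, the MCHC limit is not attainable and the MCH limit is practically never met. The documents alone do not prove that either can never be met. Nor is the high total-cholesterol limit an error because the drug lowers cholesterol, as a reader might also infer: such limits flag abnormality in either arm.

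The loss is confined to the by-arm threshold count and the flagged-patient listing that uses the same criteria. No efficacy result, alpha or power is affected. The change is worth making because it alters which patients are counted and costs almost nothing.

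**What to change.** Before unblinding, amend Table 8 and the sentence that introduces it:

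1. Replace the MCH and MCHC limits with the <0.9 x LLN / >1.1 x ULN form used for MCV.
2. Add a triglyceride row, using the protocol's 500 mg/dL (5.65 mmol/L) as a reporting threshold. State that it is read as a between-arm comparison because on-treatment samples are largely non-fasting, and identify fasting repeats where available.
3. Add PT and aPTT rows, each at a stated multiple of ULN.
4. For the remaining parameters without criteria (HDL, LDL, GGT, HbA1C, iron, LDH, MPV, RDW and urinalysis), either add limits or restrict the promise in 7.10.2 to the parameters in Table 8.

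The cost is two edited rows, three new rows and one clarified sentence. The downside is a few more flagged values, some of which will reflect meals. These are reporting thresholds only; no patient's management changes.

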7.10.3. Vital Signs

Descriptive statistics for body weight and vital signs (ie, oral temperature, respiratory rate, systolic and diastolic blood pressure, and pulse rate) and changes from baseline values at each visit will be presented by treatment group, and all the data will be listed.

The number and percentage of patients with PCS postbaseline vital signs will be tabulated by treatment group for data collecting no more than 1 day after the last dose. A vital sign value will be considered PCS if it meets both the observed value criterion and the change from baseline value criterion. The criteria for PCS vital sign values is detailed in Table 9. The percentages will be calculated relative to the number of patients with baseline values and at least 1 assessment in the corresponding postbaseline period. The numerator will be the total number of patients with available baseline values and at least 1 PCS value in the corresponding postbaseline period.

A supportive listing for patients with PCS postbaseline values will be provided, including the PID number, study center, baseline and postbaseline values for each visit, and a flag indicating the PCS vital sign values.

D		Criteria ^a				
Parameter	Flag	Observed Value	Change from Baseline			
Seated systolic blood	High	≥180	Increase of ≥20			
pressure, mmHg	Low	≤90	Decrease of ≥20			
Seated diastolic blood	High	≥105	Increase of ≥15			
pressure, mmHg	Low	≤50	Decrease of ≥15			
	High	≥120	Increase of ≥15			
Seated pulse rate, bpm	Low	≤50	Decrease of ≥15			
	High		Increase of ≥7%			
Weight, kg	Low		Decrease of ≥7%			

 Table 9:
 Criteria for Potentially Clinically Significant Vital Signs

a. A postbaseline value is considered potentially clinically significant if it meets both the criteria for observed value and the criteria for change from baseline.

bpm = beats per minute

7.10.4. ECG Parameters

Descriptive statistics for ECG variables (eg, QRS duration, QT interval, PR interval, and QTcF interval.) and their changes from baseline at each assessment time point will be presented by treatment group. ECG interpretation will be summarized by visit. A shift table from baseline to each visit for qualitative ECG results will be presented.

In addition, the number and percentage of patients with PCS postbaseline ECG will be tabulated by treatment group for data collecting no more than 1 day after the last dose. An ECG value will be considered PCS if it meets the observed value criterion. The criteria for PCS ECG values is detailed in Table 10. The percentages will be calculated relative to the number of patients with available non-PCS baseline values and at least 1 postbaseline assessment. The potential numerator will be the total number of patients with available non-PCS baseline values and at least 1 postbaseline PCS value in the corresponding post-baseline period.

A supportive listing for patients with PCS postbaseline values will be provided, including the PID number, study center, baseline and postbaseline values for each visit, and a flag indicating the PCS ECG values.

ECG Parameter	Unit	Higher Limit
QRS duration	msec	≥150
PR interval	msec	≥250
QTcF interval	msec	>500

 Table 10:
 Criteria for Potentially Clinically Significant ECG Parameters

7.10.5. Medical and Disease History

Abnormalities in patients' medical and surgical histories will be coded using the Medical Dictionary for Regulatory Activities (MedDRA), version 21.0. The number and percentage of patients with abnormalities in medical and surgical histories in each system organ class (SOC) and preferred term will be presented by treatment group and overall, for the Safety Population.

7.10.6. Physical Examination

No separate analysis for physical examinations is planned; a listing will be provided for physical examination findings.

7.11. Health Outcome Analysis

Health outcome analyses will be performed on the SA Population.

7.11.1. WPAI-Sleep Disturbance-GERD

Change from baseline in hours missed from work due to sleep disturbance from GERD as a percentage of total hours (the summation of hours missed due to sleep disturbance from GERD, hours missed due to any other reason, and hours worked) will be summarized by treatment group at Weeks 4 and 8 and analyzed using a similar MMRM approach described in Section 7.9.1.2.

Change from baseline in the effect of sleep disturbance due to GERD on work productivity and sleep disturbance due to GERD on regular daily activities other than work at a job will be summarized, respectively, by treatment group at Weeks 4 and 8 and analyzed using a similar MMRM approach described in Section 7.9.1.2.

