3.5.7.3 Study Visit Assessments

The following assessments will be performed at the study visits indicated:

• WPAI-Sleep Disturbance-GERD

The Work Productivity and Activity Impairment Questionnaire: Sleep Disturbance-GERD (WPAI-Sleep-GERD) includes questions about time lost from work, reduced productivity while at work, and reduced productivity while doing regular daily activities resulting from sleep disturbance due to GERD symptoms. Patients will complete the WPAI-Sleep-GERD at the Randomization Visit, the Week 4 Visit, and at the EOT Visit and will record their responses in the eDiary.

• EQ-5D-3L

The EuroQol (EQ)-5D-3L is a generic measure of health widely used in Europe.(13) The first component consists of 5 questions assessing the following dimensions: mobility, self-care, usual activities, pain/discomfort, and anxiety/depression. Responses to the 5 questions define a health state for which a utility index can be derived from published algorithms.(14) The

second component of the EQ-5D is a visual analogue scale, asking patients to rate their health from 0 to 100 (0 represents worst imaginable health state and 100 represents best imaginable health state). Patients will complete the EQ-5D-3L at the Randomization Visit, the Week 4 Visit, and at the EOT Visit and will record their responses in the eDiary.

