5.3. Health Outcomes Assessments

WPAI-Sleep Disturbance-GERD

The Work Productivity and Activity Impairment Questionnaire: Sleep Disturbance-GERD (WPAI-Sleep-GERD) include questions about time lost from work, reduced productivity while at work, and reduced productivity while doing regular daily activities resulting from sleep disturbance due to GERD symptoms. Patients will complete the WPAI-Sleep-GERD at the Randomization Visit, the Week 4 Visit, and at the EOT Visit and will record their responses in the eDiary.

EQ-5D-3L

The EuroQol (EQ)-5D-3L is a generic measure of health widely used in Europe (2). The first component consists of 5 questions assessing the following dimensions: mobility, self-care, usual activities, pain/discomfort, and anxiety/depression. Responses to the 5 questions define a health state. The second component of the EQ-5D is a visual analogue scale, asking patients to rate their health from 0 to 100 (0 represents worst imaginable health state and 100 represents best imaginable health state). Patients will complete the EQ-5D-3L at the Randomization Visit, the Week 4 Visit, and at the EOT Visit and will record their responses in the eDiary.

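### The WPAI work-absence percentage counts hours already lost for unrelated reasons as time at risk, which attenuates it and scores a week wholly away as an observed 0%

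*SAP*

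**What the plan says.** SAP 7.11.1 defines the first WPAI endpoint as the change from baseline in a percentage. The numerator is work hours missed because of sleep disturbance from GERD (A). The denominator is the sum of "hours missed due to sleep disturbance from GERD, hours missed due to any other reason, and hours worked". Writing O for the hours missed for unrelated reasons and W for the hours worked, the score is 100 × A/(A+O+W). The result "will be summarized by treatment group at Weeks 4 and 8 and analyzed using a similar MMRM approach described in Section 7.9.1.2". SAP 7.11 adds: "Health outcome analyses will be performed on the SA Population".

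Protocol 3.5.7.3 describes the purpose of the instrument. It "includes questions about time lost from work, reduced productivity while at work, and reduced productivity while doing regular daily activities", in each case as a result of GERD-related sleep disturbance. SAP 5.3 says the same. Neither document gives another scoring formula, a reason for the three-part denominator, or a rule for a week in which the patient had no hours available for work.

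**The concern.** The questionnaire is meant to capture time lost from work because of GERD sleep disturbance. An hour already lost to holiday or another illness cannot also be lost to sleep disturbance, so it is not time at risk. Keeping it in the denominator has two effects:

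- **Attenuation.** With A > 0 and O > 0, the score falls below the rate of loss among hours that could have been lost.
- **A false zero.** A week wholly away for an unrelated reason has A = 0, O > 0 and W = 0. It scores 0% although no work time was observed. At Week 4 or 8 the MMRM reads this as full improvement for a patient impaired at baseline. At baseline, it leaves no room to improve.

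The SAP handles comparable situations differently. Heartburn-free days are divided by diary entry days (7.9.2), and a week with no daily score has a missing WHSS (6.3). What is at stake is the size and meaning of the WPAI absence estimate.

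**Working it through.** **Inputs.** The formula comes from SAP 7.11.1. There is no stated figure to reproduce, since this is a scoring rule. The documents give neither working hours nor the frequency of unrelated absence. The following are therefore assumptions: a 40-hour week, a one-week recall period, and at-risk rates of 10% (placebo) and 6% (active).

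**1. Relation between the two scores.** The SAP score is S = A/(A+O+W) and the at-risk score is R = A/(A+W). Hence S = R × (A+W)/(A+O+W). The factor is below 1 whenever O > 0.

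**2. Single weeks of 40 hours.**

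| A | O | W | SAP rule | At-risk rule |
|---|---|---|---|---|
| 4 | 0 | 36 | 10.0% | 10.0% |
| 4 | 8 | 28 | 10.0% | 4/32 = 12.5% |
| 4 | 16 | 20 | 10.0% | 4/24 = 16.7% |
| 4 | 32 | 4 | 10.0% | 4/8 = 50.0% |
| 4 | 36 | 0 | 10.0% | 4/4 = 100% |
| 0 | 8 | 32 | 0% | 0% |
| 0 | 40 | 0 | 0% | 0/0, missing |

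The rules agree when O = 0, and also when A = 0 and W > 0.

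**3. Change from baseline**, starting from A = 4, O = 0, W = 36 (10%).

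- Week 8 with A = 2, O = 20, W = 18: the SAP rule gives 5% − 10% = −5 points. The at-risk rule gives 2/20 − 4/40 = 0.
- Week 8 with A = 0, O = 40, W = 0: the SAP rule gives −10 points. The at-risk rule gives missing.

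**4. Arm means.** If the at-risk rate does not depend on O, the SAP mean is the at-risk mean times 1 − E[O]/40. The listed O values are taken as equally likely within affected weeks.

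| Weeks with unrelated absence | O (hours) | Attenuation, E[O]/40 | Placebo mean (true 10.0%) | Difference (true 4.0 points) |
|---|---|---|---|---|
| 10% | 4, 8 | 0.10 × 6/40 = 1.5% | 9.85 | 3.94 |
| 20% | 8, 16 | 0.20 × 12/40 = 6.0% | 9.40 | 3.76 |
| 20% | 8, 16, 40 | 0.20 × 21.3/40 = 10.7% | 8.93 | 3.57 |
| 30% | 8, 16, 40 | 0.30 × 21.3/40 = 16.0% | 8.40 | 3.36 |
| 40% | 16, 40 | 0.40 × 28/40 = 28.0% | 7.20 | 2.88 |

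**5. Effect on the test.** Take whole 8-hour days, with n available days out of 5. Each is lost to GERD sleep disturbance independently with probability p (0.10 or 0.06). Use 330 per arm and a single-visit comparison. The SAP variance is p(1−p)E[n]/25 + p²Var(n)/25. The at-risk variance is p(1−p)E[1/n] among weeks with n > 0. With absence in 20% of weeks:

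| O (hours) | SAP: difference, SDs, z | At-risk: difference, SDs, z |
|---|---|---|
| 8, 16 | 3.76; 13.07, 10.33; 4.10 | 4.00; 14.02, 11.10; 4.06 |
| 8, 16, 40 | 3.57; 12.95, 10.16; 3.94 | 4.00; 13.85, 10.96; 3.97 (308 per arm) |
| 16, 32 | 3.52; 12.84, 10.08; 3.92 | 4.00; 16.25, 12.86; 3.51 |

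For example, in the second row z = 3.57/√((12.95² + 10.16²)/330) = 3.94. The SAP rule shrinks the SD along with the mean, so z barely moves. In the third row, few hours at risk make the at-risk rule noisier and z falls.

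**The case against.** The strongest defence is that the SAP states its quantity in full. Four hours lost out of 40 scheduled is 10%, whatever happened in the other hours. That stands: the figure is correct as a share of scheduled time, and no passage sets the at-risk share as the target. A reader might infer that the SAP contradicts its own documents or mis-scores the instrument. They do not support that, because neither contains a competing formula and the questionnaire form is not in the text available.

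A reader might also infer bias in favour of IW-3718, or a loss of power. Neither is supported. The rule is identical in both randomised arms, so it mainly dilutes the estimate. It would bias the comparison only if unrelated absence differed by arm, on which the documents are silent. On power, step 5 shows nearly equal test statistics in two scenarios and an advantage for the SAP rule in the third. The at-risk ratio is itself unstable when few hours remain: 4 hours lost can score 100%.

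Finally, the magnitudes rest on assumed inputs. That is true, which is why they are given as a range. None of this removes the false zero: under any of these readings, a week with no work time observed is still analysed as a measured absence of impairment.

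**Conclusion.** The concern holds as one about the size and interpretation of a supportive estimate. If the aim is absence attributable to GERD sleep disturbance, the stated denominator attenuates values with A > 0 and O > 0 by (A+W)/(A+O+W). It also turns a week wholly away into an observed 0%. Both follow from the formula alone.

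The group-level size is uncertain: about 1.5% to 28% attenuation of arm means and of the difference in points, assuming 40-hour weeks, unrelated absence in 10% to 40% of weeks, and at-risk rates independent of O. The test statistic changes little in most of the scenarios checked.

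A reader might infer a threat to the trial's main conclusions, but there is none. WPAI is outside the fixed sequence in SAP 6.6 and absent from the exploratory endpoints in SAP Table 7. The change is worth making because it is cheap and the false zero misleads.

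**What to change.** In SAP 7.11.1, define the percentage as 100 × A/(A+W), set it to missing when A+W = 0, and summarise O separately by arm and visit. The separate summary also shows whether unrelated absence is balanced between the arms.

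The cost is one sentence of text and one line of code, since all three quantities are already named as inputs. There are two small downsides. Patient-weeks with no hours at risk become missing instead of 0%. Values resting on very few at-risk hours are more variable, which can slightly reduce precision.
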